16.7 Power Calculations

The total number of patients to be recruited with an allocation ratio of 2:1 is 800 (533 VAE, 267 surgery). The total number of patients required for the re-excision comparison was 762³⁹ which has been inflated by 5%. This will ensure that we have sufficient patients for the single arm investigation into local recurrence rates with VAE, and allow for possible drop-outs. To ensure that the trial as a whole only has 5% alpha the significance level for each of the co-primary outcomes has been set at 2.5% with 90% power. The probability of success in both the surgery arm and the VAE arm is expected to be 80% (20% re-excision). The maximal acceptable difference between the two has been set at 10% which was defined as acceptable by PPI bearing in mind that this is salvageable by a second procedure and has no survival sequelae. The total number required for the local recurrence free survival outcome is 511⁴⁰ (VAE). This assumes that the expected survival probability at 5 years is 99%²⁵ and that an undesirable survival probability for VAE is 97% at 5 years. Allowing for 4 years recruitment and following all patients for a minimum of 3 years post randomisation.

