16.2 Main Trial

16.2.1 Definition of Primary outcome measures

Primary Outcome 1: Re-excision following initial procedure

The requirement for a second procedure in both arms will be ascertained.

Following VAE, patients will undergo radiological assessment of completeness of excision of their primary tumour. Where there is radiological evidence of residual disease, patients will undergo standard surgical excision (wide local excision and sentinel lymph node biopsy).

In the standard surgery arm of the trial, histopathological assessment of resection margin status will be carried out. The need for re-excision of margins will be determined by local MDT policy.

Primary Outcome 2: Local recurrence free survival time for VAE

This is defined in whole days as the time from randomisation until first report of ipsilateral invasive breast cancer. Patients without recurrence will be censored at the date of last clear mammogram or date of death.

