16.3 Analysis of Outcome Measures

Key aspects of the analysis methods to be utilised are detailed below and the statistical analysis plan will provide details of the selection of subjects to be included in each analysis in addition to procedures accounting for missing, unused or spurious data.

Primary Outcomes

Re-excision following initial procedure

Once all patients have undergone surgery the proportion of patients requiring re-excision will be compared between the trial arms. A 2-sided 95% confidence interval around the difference in proportions will be calculated. If the upper bound of the confidence interval is below 10 then non-inferiority will be declared. If non-inferiority is declared then a pre-specified but unpowered analysis of superiority will also be undertaken, to investigate whether superiority has also been demonstrated.

Local recurrence free survival time for VAE

The point estimate for local recurrence free survival at 5 years will be calculated with 2-sided 95% confidence interval using the Kaplan-Meier method. No hypothesis testing will be performed. This will be interpreted both with reference to the same rate calculated for the surgery arm of the trial and in relation to the undesirable local recurrence rate of 97%. Sensitivity analysis will be conducted utilising exact methods for calculating the proportion of recurrence at 5 years to explore the appropriateness of the Kaplan-Meier method.

Secondary Outcomes

Time to ipsilateral breast cancer recurrence, time to development of contralateral invasive breast cancer and overall survival will be analysed as per local recurrence free survival time above. Complications arising from surgery or VAE will be reported descriptively for both treatment arms (see Appendix 4 for complications and definitions). No hypothesis testing will be conducted.

QoL will be analysed using standardised area under the curve and appropriate repeated measures modelling techniques to compare treatment arms.

Page 31 of 49

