16.6 Planned Final Analyses

The final analysis of re-excision following initial procedure will be conducted 3 months following the completion of recruitment. This will ensure all patients have undergone randomised procedures and been assessed for re-excision. The analysis of complications arising from surgery or VAE will also be conducted at this point. Analysis of the local recurrence free survival and all remaining secondary outcomes will be conducted 3 months after all patients have completed 3 years of annual mammography following randomisation.

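### The stated 90% power at 2.5% for 5-year local recurrence-free survival is not delivered by a 5-year Kaplan-Meier interval computed when only about half the VAE women have reached 5 years

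*Protocol*

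**What the plan says.** Protocol section 16.7 divides the error between two co-primary outcomes: "the significance level for each of the co-primary outcomes has been set at 2.5% with 90% power". For local recurrence-free survival it assumes "the expected survival probability at 5 years is 99"% and that "an undesirable survival probability for VAE is 97% at 5 years". It requires 511 VAE women (533 are planned), with 4 years of recruitment and at least 3 years of follow-up for each woman.

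Section 16.3 fixes the estimator: "The point estimate for local recurrence free survival at 5 years will be calculated with 2-sided 95% confidence interval using the Kaplan-Meier method". It says that this estimate will not be formally tested and will be interpreted against 97% and against the surgery arm. A sensitivity analysis follows, "utilising exact methods for calculating the proportion of recurrence at 5 years".

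Section 16.2.1 sets the censoring rule: "Patients without recurrence will be censored at the date of last clear mammogram or date of death". Section 16.6 sets the date: the analysis "will be conducted 3 months after all patients have completed 3 years of annual mammography following randomisation".

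Section 7.2.3.1 schedules annual mammography for 5 years after randomisation. Section 15 says that follow-up is funded for 5 years after each woman's randomisation.

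**The concern.** The sample size and the analysis do not use the same information. An exponential model counts all person-time, so a woman followed for 7 years compensates for one followed for 3. A Kaplan-Meier estimate at 5 years gains nothing from years 6 and 7, and it loses precision from every woman censored before year 5. At the planned date those women are about half the arm or more.

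This co-primary carries the claim that the recurrence risk after VAE is acceptable. If its real power is well below 90%, a trial in which VAE performs exactly as hoped may still end with an interval that includes the undesirable rate.

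**Working it through.** **Inputs.** From section 16.7: 97% and 99% at 5 years, 2.5%, 90% power, 511 required, 533 planned, 4 years' accrual, 3 years' minimum follow-up. From section 16.6: analysis 3 months after the last woman completes 3 years. Section 16.7 does not say whether 2.5% is one- or two-sided; a 2-sided 95% interval has 2.5% on each side. Assumptions not in the protocol: exponential recurrence times, no deaths or dropout.

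**Step 1: the stated 511.** The hazards are λ0 = -ln(0.97)/5 = 0.00609 and λ1 = -ln(0.99)/5 = 0.00201 per year. With even accrual over A = 4 years and minimum follow-up F, the event probability is p = 1 - [exp(-λF) - exp(-λ(A+F))]/(λA). For F = 3 this gives p0 = 0.0300 and p1 = 0.0100.

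- Exact Poisson event count, one-sided 2.5%, F = 3: N = 526. Up to 8 events has probability 2.5% under 97% and 91% under 99%.
- Hazard scale, one-sided 2.5%, F = 3.25: N = [(1.960·λ0/√p0 + 1.282·λ1/√p1)/(λ0 - λ1)]² = 513.
- Log-hazard scale, two-sided 2.5%, F = 3: N = [(2.241 + 1.282)/ln(λ0/λ1)]² / 0.0200 = 505.

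So 511 is consistent with an exponential calculation. Which variant was used cannot be identified. Simple proportions with everyone followed to 5 years give 533 (normal approximation) or 481 (arcsine).

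**Step 2: who has reached 5 years.** The last woman completes 3 years at month 84, so the analysis falls at month 84 to 87. A woman has 5 years' follow-up if she was randomised by month 24 to 27.

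- Even accrual over 48 months: 24/48 = 50% to 27/48 = 56%.
- Slower start, with 141 of 800 in 18 months (the pilot target in section 16.1.3) and the other 659 evenly over 30 months: (141 + 6 × 659/30)/800 = 34% to (141 + 9 × 659/30)/800 = 42%.

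**Step 3: precision lost.** With even accrual and F = 3, the share still under follow-up at time u is 1 up to 3 years and (7 - u)/4 after that. For rare events the Greenwood variance grows by (3 + 4·ln 2)/5 = 1.155 compared with complete 5-year follow-up. About 533 × 0.5 × 0.99 = 264 women are at risk at 5 years. Expected recurrences under 99% are only about 533 × 0.01 = 5, so the form of the interval also matters.

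**Step 4: operating characteristics.** These are simulated trials of 533 women. Success is taken as a lower 95% limit above 97%.

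| Reading of the 5-year Kaplan-Meier estimate | Power at 99% | Error at 97% |
|---|---|---|
| Log-log, even accrual, 3-3.25 years' minimum | 80-82% | 1.6-1.7% |
| Log-log, censored at last clear mammogram | 74-78% | 1.7-1.9% |
| Arcsine, even or slower accrual | 87-92% | 3.6-4.3% |
| Plain Greenwood | 92-95% | 5.5-6.3% |
| Cut-off calibrated to 2.5% | 85-89% | 2.5% |
| Log-log, all 533 followed to 5 years | 91% | 2.0% |

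The last row can be checked directly. With complete follow-up, success corresponds to at most 8 recurrences in 533. The binomial probability of that is 0.909 at a 1% risk and 0.021 at a 3% risk.

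None of the first five rows gives 90% power together with 2.5% error. With 3 years' minimum follow-up, the log-log interval would need about 660 VAE women for 90%.

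**The case against.** Four points on the other side carry weight.

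- **No decision rule.** Section 16.3 disclaims testing and reads the estimate against the surgery arm as well as 97%. A lower limit above 97% is the natural reading, but it is not the protocol's text. This stands as a limit on the figures. It does not rescue the power statement: section 16.7 assigns error and power to this outcome, and without a criterion the 90% has no meaning.
- **Interval type belongs in the SAP.** This is true, and its absence here is no error. A reader might infer that the trial runs more than twice its stated risk of accepting an undesirable recurrence rate. The documents do not support that: it arises only with a plain interval, which the SAP may not use. Since none of the intervals examined delivers the stated pair at the planned date, however, the choice cannot repair section 16.7.
- **Short follow-up is not the whole cause.** With about 5 expected events, the log-log interval is conservative in its own right. Even 511 women all followed for 5 years give only 85.5% with it. At 533, the shorter follow-up costs about 11 points with log-log (91% to 80%). With a cut-off calibrated to 2.5% it costs less (about 91% to 85-89%).
- **The number 511 is not wrong.** It reproduces to within about 3%. The fault lies in matching it to this estimator at this date.

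A reader might also take the exact-proportion sensitivity analysis as invalid in itself. Section 16.3 fixes no denominator, so that goes too far; the analysis is simply easier to interpret once every woman has reached 5 years.

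**Conclusion.** The point holds in this form: the planned analysis at the planned date does not deliver the stated 90% power at 2.5% error. With 533 VAE women, power is about 74-82% for a log-log interval that respects 2.5%, and about 85-89% even for a cut-off tuned to exactly 2.5%. Intervals that reach about 90% or more do so with error of about 4-6%.

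The figures rest on exponential recurrence, no dropout or deaths, accrual that is even or starts slowly, and reading the 95% limit against 97%. Dropout would lower the power further. If 2.5% is meant as two-sided, so that a 97.5% interval applies, log-log power falls to about 63% (even accrual, 3 years' minimum).

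Short follow-up and few events both contribute. Complete 5-year follow-up of the planned 533 restores about 90-91% power with error of about 2-2.5%. A reader might also infer that the trial misses a promised joint power for both co-primaries, but section 16.7 claims 90% for each outcome separately, so that is no discrepancy.

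**What to change.** 1. In section 16.7, restate the power of this co-primary at the planned date as about 75-82% (log-log interval read against 97%, with accrual and censoring assumptions given). Reconcile the exponential sizing with the Kaplan-Meier analysis at 5 years.
2. In section 16.6, name the analysis after all women have completed the year-5 mammogram as the definitive analysis of this co-primary. Label the analysis at 3 years' minimum follow-up as early. Run the exact-proportion sensitivity analysis of section 16.3 at the later date.

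As a suggestion for the SAP rather than a protocol correction, a log-log interval keeps the error within 2.5% with so few events.

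The cost is wording and a less favourable power statement. No extra women or visits are needed, because the mammograms are scheduled to year 5 and follow-up to that point is funded. The definitive answer comes up to 2 years later, with the early analysis still available meanwhile.

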17. TRIAL ORGANISATIONAL STRUCTURE

17.1 Sponsor

The study is sponsored by the University of Birmingham.

17.2 Coordinating Centre

The trial is being conducted under the auspices of the Cancer Research UK Clinical Trials Unit (CRCTU), University of Birmingham according to their local procedures.

17.3 Trial Management Group

The Chief Investigator, Co-investigators, Trial Statistician, Senior Trial Manager and Trial Coordinator will form the TMG (members are identified in the introductory pages). The TMG will be responsible for the day-to-day conduct of the trial. They will be responsible for the clinical set-up, promotion, on-going management of the trial, the interpretation of the results and preparation and presentation of relevant publications. The TMG will meet every 3 months (usually by teleconference).

17.4 Trial Steering Committee

The TSC will be set up to provide overall supervision of the study, safety monitoring and to ensure the study is being conducted in accordance with the principles of GCP. Membership will be composed of the TMG, independent clinicians, invited Principal Investigators, representatives from the funders, an independent chair and at least one patient advocate. The TSC will meet shortly before commencement of the trial and then annually (usually by teleconference); they will supervise the conduct of the trial, monitoring progress including recruitment, data completeness, losses to follow-up, and deviations from the protocol. They will make recommendations about conduct and continuation of the study.

17.5 Data Monitoring Committee

Data analyses will be supplied in confidence to an independent Data Monitoring Committee (DMC), which will be asked to give advice on whether the accumulated data from the trial, together with the results from other relevant research, justifies the continuing recruitment of further patients. The DMC will operate in accordance with a trial specific charter based upon the template created by the Damocles Group. The DMC will is scheduled to meet 6, 12 18 and 24 months after the trial opens to recruitment and then annually during the main recruitment phase and subsequently as and when required. Additional meetings may be called if recruitment is much faster than anticipated and the DMC may, at their discretion, request to meet more frequently or continue to meet following completion of recruitment. An emergency meeting may also be convened if a safety issue is identified. The DMC will report directly to the TMG who will convey the findings of the DMC to TSC, funder, and/or Sponsor as applicable. The DMC may consider recommending the discontinuation of the trial if the recruitment rate or data quality are unacceptable or if any issues are identified which may compromise patient safety. The trial would also stop early if the interim analyses showed differences between treatments that were deemed to be convincing to the clinical community.

17.6 Finance

SMALL is a clinician-initiated and clinician-led trial funded by the National Institute for Health Research Health Technology Assessment Programme. The study has been independently peer reviewed and has been adopted by the National Institute for Health Research (NIHR) Clinical Research Network (CRN) Portfolio.

The Sponsor will pay Research Costs, as defined in the Clinical Site Agreement, to participating sites.

18. ETHICAL CONSIDERATIONS

The trial will be performed in accordance with the recommendations guiding physicians in biomedical research involving human subjects, adopted by the 18th World Medical Association General Assembly, Helsinki, Finland, 1964, amended by the 48th WMA General Assembly, Somerset West, Republic of South Africa, 1996.

The trial will be conducted in accordance with the UK Policy Framework for Health and Social Care Research and the General Data Protection Regulation and Human Tissue Act 2018 if appropriate) and Good Clinical Practice (GCP). The protocol will be submitted to and approved by the main Research Ethics Committee (REC) prior to circulation.

Before any patients are enrolled into the trial, the Principal Investigator at each site is required to obtain local R&D approval. Sites will not be permitted to enrol patients until written confirmation of R&D approval is received by the Trial Office.

It is the responsibility of the Principal Investigator to ensure that all subsequent amendments gain the necessary local approval. This does not affect the individual clinicians' responsibility to take immediate action if thought necessary to protect the health and interest of individual patients.

19. CONFIDENTIALITY AND DATA PROTECTION

Personal data recorded on all documents will be regarded as strictly confidential and will be handled and stored in accordance with the General Data Protection Regulation and the Data Protection Act (2018). With the patient's consent, their full name, date of birth, National Health Service (NHS) number, or in Scotland the Community Health Index (CHI), address, post code and hospital number will be collected at trial entry to allow the Trial Office to send patient questionnaires to the patient's home address and for the purposes of tracing through NHS Digital. Patients will be identified using only their unique TNO, initials and date of birth on the Case Report Form and correspondence between the Trial Office to be sent a copy of their signed Informed Consent Form which will not be anonymised. This will be used to perform in-house monitoring of the consent process and may also be forwarded to other health care professionals involved in the treatment of the patient (e.g. patient's GP).

The Investigator must maintain documents not for submission to the Trial Office (e.g. Patient Identification Logs) in strict confidence. In the case of specific issues and/or queries from the regulatory authorities, it will be necessary to have access to the complete trial records, provided that patient confidentiality is protected.

The Trial Office will maintain the confidentiality of all patients' data and will not disclose information by which patients may be identified to any third party other than those directly involved in the treatment of the patient and organisations for which the patient has given explicit consent for data transfer (e.g. Cancer Registries, laboratory staff. Representatives of the SMALL trial team may be required to have access to patient's notes for quality assurance purposes but patients should be reassured that their confidentiality will be respected at all times.

20. INSURANCE AND INDEMNITY

University of Birmingham employees are indemnified by the University insurers for negligent harm caused by the design or co-ordination of the clinical trials they undertake whilst in the University's employment.

In terms of liability at a site, NHS Trust and non-Trust hospitals have a duty to care for patients treated, whether or not the patient is taking part in a clinical trial. Compensation is therefore available via NHS indemnity in the event of clinical negligence having been proven.

The University of Birmingham cannot offer indemnity for non-negligent harm. The University of Birmingham is independent of any pharmaceutical company, and as such it is not covered by the Association of the British Pharmaceutical Industry (ABPI) guidelines for patient compensation.

21. PUBLICATION POLICY

Results of this trial will be submitted for publication in a peer reviewed journal. The manuscript will be prepared by the Trial Management Group (TMG) and authorship will be determined by mutual agreement.

Any secondary publications and presentations prepared by Investigators must be reviewed by the TMG. Manuscripts must be submitted to the TMG in a timely fashion and in advance of being submitted for publication, to allow time for review and resolution of any outstanding issues. Authors must acknowledge that the trial was performed with the support of the University of Birmingham. Intellectual property rights will be addressed in the Clinical Study Site Agreement between Sponsor and site.

Page 34 of 49

APPENDIX 1 – WMA DECLARATION OF HELSINKI

Recommendations guiding physicians in biomedical research involving human subjects

Adopted by the 18th World Medical Assembly Helsinki, Finland, June 1964 and amended by the 29th World Medical Assembly, Tokyo, Japan, October 1975, 35th World Medical Assembly, Venice, Italy, October 1983, 41st World Medical Assembly, Hong Kong, September 1989 and the 48th General Assembly, Somerset West, Republic of South Africa, October 1996

INTRODUCTION

It is the mission of the physician to safeguard the health of the people. His or her knowledge and conscience are dedicated to the fulfilment of this mission.

The Declaration of Geneva of the WMA binds the physician with the words, "The Health of my patient will be my first consideration," and the International Code of Medical Ethics declares that, "A physician shall act only in the patient's interest when providing medical care which might have the effect of weakening the physical and mental condition of the patient."

The purpose of biomedical research involving human subjects must be to improve diagnostic, therapeutic and prophylactic procedures and the understanding of the aetiology and pathogenesis of disease.

In current medical practice most diagnostic, therapeutic or prophylactic procedures involve hazards. This applies especially to biomedical research.

Medical progress is based on research which ultimately must rest in part on experimentation involving human subjects.

In the field of biomedical research a fundamental distinction must be recognized between medical research in which the aim is essentially diagnostic or therapeutic for a patient, and medical research, the essential object of which is purely scientific and without implying direct diagnostic or therapeutic value to the person subjected to the research.

Special caution must be exercised in the conduct of research which may affect the environment, and the welfare of animals used for research must be respected.

Because it is essential that the results of laboratory experiments be applied to human beings to further scientific knowledge and to help suffering humanity, the WMA has prepared the following recommendations as a guide to every physician in biomedical research involving human subjects. They should be kept under review in the future. It must be stressed that the standards as drafted are only a guide to physicians all over the world. Physicians are not relieved from criminal, civil and ethical responsibilities under the laws of their own countries.

I. BASIC PRINCIPLES

- 7. Biomedical research involving human subjects must conform to generally accepted scientific principles and should be based on adequately performed laboratory and animal experimentation and on a thorough knowledge of the scientific literature.
- 8. The design and performance of each experimental procedure involving human subjects should be clearly formulated in an experimental protocol which should be transmitted for consideration, comment and guidance to a specially appointed committee independent of the investigator and the sponsor provided that this independent committee is in conformity with the laws and regulations of the country in which the research experiment is performed.
- 9. Biomedical research involving human subjects should be conducted only by scientifically qualified persons and under the supervision of a clinically competent medical person. The responsibility for the human subject must always rest with a medically qualified person and never rest on the subject of the research, even though the subject has given his or her consent.

Page 38 of 49

- 10. Biomedical research involving human subjects cannot legitimately be carried out unless the importance of the objective is in proportion to the inherent risk to the subject.
- 11. Every biomedical research project involving human subjects should be preceded by careful assessment of predictable risks in comparison with foreseeable benefits to the subject or to others. Concern for the interests of the subject must always prevail over the interests of science and society.
- 12. The right of the research subject to safeguard his or her integrity must always be respected. Every precaution should be taken to respect the privacy of the subject and to minimize the impact of the study on the subject's physical and mental integrity and on the personality of the subject.
- 13. Physicians should abstain from engaging in research projects involving human subjects unless they are satisfied that the hazards involved are believed to be predictable. Physicians should cease any investigation if the hazards are found to outweigh the potential benefits.
- 14. In publication of the results of his or her research, the physician is obliged to preserve the accuracy of the results. Reports of experimentation not in accordance with the principles laid down in this Declaration should not be accepted for publication.
- 15. In any research on human beings, each potential subject must be adequately informed of the aims, methods, anticipated benefits and potential hazards of the study and the discomfort it may entail. He or she should be informed that he or she is at liberty to abstain from participation in the study and that he or she is free to withdraw his or her consent to participation at any time. The physician should then obtain the subject's freely-given informed consent, preferably in writing.
- 16. When obtaining informed consent for the research project the physician should be particularly cautious if the subject is in a dependent relationship to him or her or may consent under duress. In that case the informed consent should be obtained by a physician who is not engaged in the investigation and who is completely independent of this official relationship.
- 17. In case of legal incompetence, informed consent should be obtained from the legal guardian in accordance with national legislation. Where physical or mental incapacity makes it impossible to obtain informed consent, or when the subject is a minor, permission from the responsible relative replaces that of the subject in accordance with national legislation. Whenever the minor child is in fact able to give a consent, the minor's consent must be obtained in addition to the consent of the minor's legal guardian.
- 18. The research protocol should always contain a statement of the ethical considerations involved and should indicate that the principles enunciated in the present Declaration are complied with.

II. MEDICAL RESEARCH COMBINED WITH PROFESSIONAL CARE

(Clinical Research)

- In the treatment of the sick person, the physician must be free to use a new diagnostic and therapeutic measure, if in his or her judgement it offers hope of saving life, reestablishing health or alleviating suffering.
- 19. The potential benefits, hazards and discomfort of a new method should be weighed against the advantages of the best current diagnostic and therapeutic methods.
- 20. In any medical study, every patient including those of a control group, if any should be assured of the best proven diagnostic and therapeutic method. This does not exclude the use of inert placebo in studies where no proven diagnostic or therapeutic method exists.
- 21. The refusal of the patient to participate in a study must never interfere with the physician-patient relationship.

- 22. If the physician considers it essential not to obtain informed consent, the specific reasons for this proposal should be stated in the experimental protocol for transmission to the independent committee (I,
- 23. The physician can combine medical research with professional care, the objective being the acquisition of new medical knowledge, only to the extent that medical research is justified by its potential diagnostic or therapeutic value for the patient.

III. NON-THERAPEUTIC BIOMEDICAL RESEARCH INVOLVING HUMAN SUBJECTS (Non-Clinical Biomedical Research)

- 2) In the purely scientific application of medical research carried out on a human being, it is the duty of the physician to remain the protector of the life and health of that person on whom biomedical research is being carried out.
- 24. The subject should be volunteers either healthy persons or patients for whom the experimental design is not related to the patient's illness.
- 25. The investigator or the investigating team should discontinue the research if in his/her or their judgement it may, if continued, be harmful to the individual.
- 26. In research on man, the interest of science and society should never take precedence over considerations related to the wellbeing of the subject.

